11.5 General Statistical Considerations

Statistical analyses will use a two-tailed test and will be evaluated at an α of 0.05 unless otherwise specified. The mean, standard deviation (SD), median, minimum and maximum will be presented for continuous variables such as participant age. For categorical variables, such as sex, the number for each category, the total number evaluated, and the percentage will be presented.

11.6 Participant Accountability and Missing Data

Participants who withdraw from the study will be tabulated with the reasons for the withdrawal. A sensitivity analysis of the FAS population will only be conducted if $\geq 5\%$ of the primary effectiveness results are missing. The imputation method is described below in the Effectiveness Analyses section. Missing data will not be imputed for the PP or Safety populations.

11.7 Participant Demographic and Baseline Characteristics

The demographic and baseline characteristics of the study population observed will be presented descriptively.

11.8 Effectiveness Analyses

The primary effectiveness variable will be the change in EDS between the time point preceding application and the subsequent time point following application. The primary effectiveness endpoint will be the analysis of the primary effectiveness variable for the FAS population at Day

45 without imputation. The analysis will use a paired *t*-test or Wilcoxon signed-rank test, as appropriate, and will be evaluated at a one-sided α of 0.025. If $\geq 5\%$ of the FAS population is missing the primary effectiveness variable at Day 45, a sensitivity analysis of EDS difference at Day 45 will be performed by imputing the missing EDS difference as zero. Study participants with a missing Day 45 result will be imputed one at a time and the analysis will be repeated. This process will continue until either the result is no longer statistically significant or all participants with missing results have been imputed. As an additional sensitivity analysis, missing values will be imputed using a random selection process from the available Day 45 results and the analysis will be repeated. This process will be performed 10 times and a single combined p-value for the 10 imputations will be obtained by a method described in Rubin³⁸ and in the SAS manual for PROC MIANALYZE.³⁹ If the study includes more than one site, summaries of the primary effectiveness endpoint without imputation will be presented by site.

The primary effectiveness analysis will be repeated in the PP population as a sensitivity analysis.

The exploratory effectiveness variables will be the difference in EDS at Day 0, the difference in dry eye discomfort using the [REDACTED] Calibra scale in the FAS population at Day 0 and Day 45 and the difference in Schirmer test results at Day 7. The analysis will be performed using the same method as the primary effectiveness variable. Statistical significance will be determined using a one-sided test at an α of 0.025.

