11.0 STATISTICAL HYPOTHESIS AND METHODS OF ANALYSES

11.1 Power Calculation and Determination of Sample Size

In a previous controlled study assessing the change in EDS while in the CAE at Day 0, the observed mean (SD) treatment difference for the TrueTear device compared to the control was -13.4 (23.9). It is unknown what, if any, effect on the change in EDS while in the CAE will be with the TrueTear device application after 45 days of use. Using an estimated standard deviation of 25, 45 participants will provide over 90% power to detect a EDS reduction of 13 based on a one-sided test at an α of 0.025.

In the previous study, approximately 10% of the participants did not reach the application threshold during the CAE session. In order to allow for participants that discontinue the study before Day 45 or do not reach the application threshold in the CAE, approximately 60 qualified participants will be identified to initiate the study to ensure Day 45 results for 45 participants.

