11.4 Evaluability of Data

All participants who initiated at least one study application will be eligible for inclusion in the analyses. Participation in the study will be summarized by presenting the number of participants who were enrolled, the number of participants who completed the study, and the number of participants who did not complete the study due to not reaching the threshold or by reason of early discontinuation.

Full Analysis Set Population (FAS): The FAS population will include all participants who initiated at least one application of the TrueTear device at any point during the study.

Per protocol population (PP): The PP population is a subset of the FAS population, which did not have a major protocol deviation likely to seriously affect the primary outcome of the study. This population will be the secondary population for the effectiveness analyses and will also be used to summarize the primary and exploratory effectiveness variables. If the PP and FAS populations are exactly the same, then additional efficacy analyses on the PP population will not be performed.

Safety Population: The safety population will be the same as the FAS population.

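### The zero-imputation sensitivity analysis is close to inert: it would call a significant Day 45 result robust almost however many values are missing, and the test it uses is not fixed

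*Combined protocol and SAP*

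**What the plan says.** Section 11.8 (Effectiveness Analyses) sets out the primary analysis and two sensitivity analyses.

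- **Primary test.** A paired t-test or "Wilcoxon signed-rank test, as appropriate, and will be evaluated at a one-sided" level of 0.025, in the FAS at Day 45, without imputation. The available text gives no criterion for choosing between the two tests.
- **Sensitivity analysis 1.** If 5% or more of the FAS lacks the Day 45 value, the analysis is "performed by imputing the missing EDS difference as zero". Participants are imputed one at a time, and the test is repeated until significance is lost or nobody is left to impute.
- **Sensitivity analysis 2.** Missing values are drawn at random from the observed Day 45 results 10 times, and "a single combined p-value for the 10 imputations will be obtained by a method described in" the cited multiple-imputation reference and software manual.

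Section 11.4 defines the FAS as "all participants who initiated at least one application of the TrueTear device at any point during the study", so participants without a Day 45 result stay in it. Section 11.1 gives the design figures: "Using an estimated standard deviation of 25, 45 participants will provide over 90% power to detect a EDS reduction of 13". It adds that "approximately 60 qualified participants will be identified to initiate the study to ensure Day 45 results for 45 participants", and that in the previous study "approximately 10% of the participants did not reach the application threshold during the CAE session".

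**The concern.** A stress test for missing data should be able to overturn a fragile result. This one replaces each unknown difference by the same constant. The mean moves towards zero, but the spread falls and the sample size rises, and these changes nearly cancel in the test statistic. The usual form of the signed-rank test discards zero differences, so there the added zeros do nothing at all.

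The analysis is likely to be run. The trigger is 5% of about 60 participants, that is 3. The plan itself expects about 10% not to reach the application threshold, and its enrolment target allows for 15 of 60 (25%) without a Day 45 result. A report that significance survived imputation of every missing participant would read as strong evidence of robustness when it says very little.

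The open choice of test adds to this. The plan does not say how zeros are handled in the signed-rank test, or which estimate and standard error would be combined across imputations if that test were used.

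**Working it through.** **Inputs.** From Section 11.1: n = 45 observed, SD 25, reduction 13, one-sided α 0.025, about 60 enrolled (hence 15 missing). Observed means of 10, 8 and 7.6 are assumed, to show less comfortable results. The shape of the distribution of changes is not in the documents, so every shape below is an assumption. Relief is counted as positive.

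**1. The plan's power.** Noncentrality = (13/25) × √45 = 3.488 with 44 df, which gives power of 92.7%. The stated figure of over 90% is reproduced for a paired t-test on the mean.

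**2. Constant zeros under the t-test.** With k zeros added and N = 45 + k:

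- new mean M = 45m/N
- sum of squares SS = 44 × 625 + 45m² − N·M²
- t = M / √(SS / [(N − 1)N])

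For m = 10 and k = 15: M = 7.5; SS = 27,500 + 4,500 − 3,375 = 28,625; SD = √(28,625/59) = 22.03; SE = 22.03/√60 = 2.844; t = 2.637. Before imputation the SE was 25/√45 = 3.727 and t was 2.683. The mean fell by 25% and the SE by about 24%.

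| Observed mean | t, no zeros | t, 15 zeros | p, no zeros | p, 15 zeros |
|---|---|---|---|---|
| 13 | 3.49 | 3.38 | 0.00056 | 0.00064 |
| 10 | 2.68 | 2.64 | 0.0051 | 0.0053 |
| 8 | 2.147 | 2.125 | 0.0187 | 0.0189 |
| 7.6 | 2.04 | 2.02 | 0.0237 | 0.0239 |

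As k grows without limit, t tends to 45m / √(27,500 + 45m²). At m = 8 this is 360/√30,380 = 2.065, a one-sided p of about 0.019. On these figures no number of zeros would remove significance.

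**3. Constant zeros under the signed-rank test** (45 simulated values scaled to SD 25, 15 zeros added).

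| Zero handling | Example with mean 13 | Example with mean 8 |
|---|---|---|
| Dropped | 0.00054 → 0.00054 | 0.01814 → 0.01814 |
| Pratt | 0.00054 → 0.00098 | 0.01814 → 0.01347 |
| Split | 0.00054 → 0.00105 | 0.01814 → 0.01398 |

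With zeros dropped, the stopping rule can never take effect. With the other conventions p rose in one example and fell in the other.

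**4. Zero-mean draws with the observed SD.** Fifteen values are drawn from a normal distribution with mean 0 and SD 25, with 10 imputations, and the mean and its SE are combined by Rubin's rules. Using expected values at m = 10:

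- pooled mean = 0.75 × 10 = 7.5
- between-imputation variance B = 15 × 625/60² = 2.604
- within-imputation variance U = [27,500 + 4,500 + 9,375 − 60 × (7.5² + 2.604)]/(59 × 60) = 10.690
- total variance T = 10.690 + 1.1 × 2.604 = 13.555, SE 3.682
- t = 7.5/3.682 = 2.037 on about 200 df, p = 0.0215

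Simulation agrees: median p about 0.021, with about a third of runs above 0.025. At m = 8 the same steps give U = 10.576, T = 13.441, t = 6/3.666 = 1.637 and p of about 0.052, against 0.0189 with constant zeros.

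**5. Error rate of the open choice at n = 45** (100,000 simulated trials per shape, 40,000 for the pre-test rule; null with mean zero).

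| Shape | t | Wilcoxon | Smaller p taken | Shapiro-Wilk rule |
|---|---|---|---|---|
| Normal | 2.50% | 2.44% | 2.92% | 2.56% |
| t, 3 df | 2.25% | 2.40% | 3.09% | 2.46% |
| Laplace | 2.46% | 2.44% | 3.23% | 2.49% |
| Uniform | 2.61% | 2.53% | 2.74% | 2.55% |
| Gamma(4), left skew | 4.00% | 8.27% | 8.32% | 7.80% |
| Exponential, left skew | 5.65% | 20.75% | 20.77% | 20.77% |

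Mirror-image right skew puts every column below 2.5%.

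**The case against.** Three stronger readings are tempting, and the documents do not support them.

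- **That leaving the test open raises the error rate.** The plan says the test is chosen as appropriate. It does not say that the smaller p-value is reported. Under a result-blind normality rule with symmetric data, the error stays at 2.46% to 2.56%. The rates of 8% and 21% need left-skewed relief with mean zero, and Wilcoxon alone produces almost all of them, because it then tests a different null from the mean. The documents give an SD and no shape.
- **That neither missing-data analysis works if Wilcoxon is used.** Zero imputation is exactly inert only if zeros are dropped, which the plan does not state. The combination step is under-specified rather than impossible. In one worked example, pooling the standardised signed-rank statistic with variance 1 gave p = 0.009, against 0.011 for the mean.
- **That fixing the test cures the problem.** It does not, because constant zeros are nearly inert under the t-test as well.

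It is also fair to say that the primary analysis uses no imputation, so a weak sensitivity analysis does not affect primary type I error. That stands. What remains is that the stated stress test cannot do its job under either permitted test.

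**Conclusion.** The concern holds for the zero-imputation rule. With 45 observed values, SD 25 and 15 missing, the rule moves the t-test p-value by about 0.0002 or less at each mean examined. It leaves the signed-rank p-value unchanged when zeros are dropped. It would report a significant result as robust almost regardless of how much is missing. Giving the imputed values realistic spread raises p from about 0.005 to about 0.021 at an observed mean of 10, and from about 0.019 to about 0.052 at a mean of 8.

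The unfixed choice of test is a secondary, conditional weakness. It raises one-sided error to about 2.7% to 3.2% with symmetric data if the smaller p is taken, and to more if relief is left-skewed and Wilcoxon is used against a mean null. With symmetric data and a result-blind rule the increase is essentially nil.

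These sizes rest on the planned SD and sample size, the full allowance of 15 missing, and assumed distribution shapes. This should be changed, but it does not invalidate the primary analysis.

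**What to change.** 1. Replace the constant zeros by multiple imputation from a distribution with mean 0 and the observed SD, applied to all participants with a missing Day 45 value. Combine the mean and its standard error by Rubin's rules. Fix the seed in advance and use more than 10 imputations, since with the observed data held fixed the spread of p between runs is imputation noise.
2. Name the paired t-test on the mean change as the single primary test. This matches the mean and SD terms of Section 11.1 and keeps power at 92.7%. Use it in both missing-data analyses.
3. Keep the signed-rank test as supportive only, and state how it handles zeros.

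The cost is SAP wording and a few lines of code. There are three drawbacks. The t-test is slightly less efficient if changes are heavy-tailed. It is itself above 2.5% under left skew (4.0% and 5.7% in the shapes tried), so naming it does not restore exact control there. The sensitivity result will be less favourable than under constant zeros.

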5.6 Discontinuation Criteria (if applicable)

Participants are free to discontinue their participation in this study at any time and for any reason, specified or unspecified, without prejudice. In addition, the Investigator may decide to

discontinue a participant from the study for safety reasons or when it is in the best interest of the participant. No constraints will be placed on ordinary patient management.

Reasons for participant withdrawal may include but are not limited to the following:

- Either at the Investigator's request, for safety reasons (e.g., serious or severe AE), or at the participant's request
- Non-compliance (e.g., failure to follow application instructions, missing visits, using prohibited medications)
- When a concomitant therapy likely to interfere with the results of the study is reported or required by the participant (the Investigator will report all such information on the source documents/ case report forms (CRFs) and decide, in accordance with the Sponsor, whether the participant is to be withdrawn)
- A confirmed positive pregnancy test at any time during the study
- When a participant is lost to follow-up. The Investigator (or designee) will attempt three times to reach the participant by telephone, and will send a follow-up letter by certified mail before considering the participant as lost to follow-up. These actions will be documented and recorded on the End of Study CRF and a copy of the follow-up letter maintained in the Investigator's file.
- When a participant is erroneously admitted into the study or does not meet the eligibility criteria

In addition, the Sponsor also reserves the right to discontinue the study at any time for clinical or administrative reasons.

All early discontinuations and their reasons should be carefully documented by the Investigator on the End of Study CRF and, if applicable, on the Adverse Event (AE) CRF. Notification of a participant's discontinuation and the reason for discontinuation will be made to [REDACTED] and/or Sponsor. No participant who has entered the CAE at Day 0 can be replaced by another participant if the participant is discontinued prematurely for any reason. Participants who terminate early will be asked to complete safety assessments (if the participant agrees) prior to study exit.

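### The zero-imputation check almost cannot fail: with 45 observed changes, no t-test result with one-sided p below 0.0244 can be overturned, and no planned analysis assumes worsening among the missing

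*Combined protocol and SAP*

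**What the plan says.** Section 11.8 makes the primary analysis the FAS at Day 45 without imputation, by paired t-test or Wilcoxon signed-rank test at one-sided 0.025. Three supporting analyses are planned, the first two only if at least 5% of the FAS lacks the result:

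- **Zero loop.** "a sensitivity analysis of EDS difference at Day 45 will be performed by imputing the missing EDS difference as zero". Zeros are added one participant at a time: "This process will continue until either the result is no longer statistically significant or all participants with missing results have been imputed". Retained significance is the only stated criterion.
- **Random draws.** "missing values will be imputed using a random selection process from the available Day 45 results", 10 times, combined by Rubin's method.
- **Per-protocol repeat.** Section 11.6 states: "Missing data will not be imputed for the PP or Safety populations".

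Missing results are provided for. Section 11.1 says "approximately 60 qualified participants will be identified to initiate the study to ensure Day 45 results for 45 participants", and reports that in the previous study "approximately 10% of the participants did not reach the application threshold during the CAE session". Section 5.6 lists withdrawal "for safety reasons (e.g., serious or severe AE") and for not following the application instructions, and adds: "No participant who has entered the CAE at Day 0 can be replaced by another participant". The section on early termination asks those who stop early for safety and pre-CAE evaluations only, so they supply no in-CAE change.

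**The concern.** A zero for each missing participant looks like a cautious no-benefit assumption. But giving every missing participant exactly the same value adds observations with no spread of their own. The estimate falls, and its standard error falls nearly as fast. A check judged only by significance then passes almost automatically, and the report could offer that pass as evidence of robustness.

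The other two analyses do not fill the gap. Random draws give the missing, on average, the completers' benefit, and the PP repeat imputes nothing. No analysis centres the missing on worsening, and none combines no relief with realistic spread. Some listed withdrawal reasons could be related to outcome, and a single-arm test against zero has no control group in which similar dropout might offset the bias.

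**Working it through.** **Inputs.** From section 11.1: n = 45 observed, SD 25, mean reduction 13 mm, one-sided α 0.025, about 60 starters. Positive values mean relief, as in section 11.2.

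**The plan's own figure.** Noncentral t with 44 df and noncentrality (13/25)√45 = 3.488 gives power 92.7%, so the stated power of over 90% reproduces.

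**Algebra of the loop.** Let S = Σd, Q = Σd² and c = S²/Q over the observed changes. Zeros change neither S nor Q. With N participants in total (observed plus zeros),

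t² = (N−1)S² / (NQ − S²) = (N−1)c / (N−c).

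As N grows, t² falls only to c. This holds whatever the shape of the data.

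**Numbers.** S = 45 × mean; Q = 44 × 625 + 45 × mean².

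| Observed mean | c | t, no zeros (p) | t, 15 zeros (p) | Limit √c (p) | Mean after 15 zeros |
|---|---|---|---|---|---|
| 13 | 342,225/35,105 = 9.749 | 3.488 (0.00056) | 3.383 (0.00064) | 3.122 (0.0009) | 9.75 |
| 8 | 129,600/30,380 = 4.266 | 2.147 (0.0187) | 2.125 (0.0189) | 2.065 (0.0194) | 6.00 |

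**Cut-off.** Setting c = 1.96² and solving back at N = 45 gives t = 2.0265, p = 0.0244, an observed mean of 7.55 mm. The critical value with no zeros is 2.0154, or 7.51 mm. Unlimited zeros can therefore flip only means between 7.51 and 7.55 mm, which has probability 0.16% at the planning values. With 9 or 15 zeros the window is 7.51 to 7.52 mm, with probability 0.03% to 0.04%. The limiting cut-off is 0.0240 for 30 observed and 0.0245 for 55, so the conclusion does not hinge on 45. A signed-rank test that discards zeros does not move at all.

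**Missing share (an allowance, not a forecast).** 60 − 45 = 15, or 25% of 60. If about 10% of 60 = 6 never apply the device and fall outside the FAS, 9 of 54 = 17% are missing. The visible text does not settle which applies. Both exceed the 5% trigger.

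**Comparison: no mean relief, spread kept.** Assume m missing with mean 0 and SD 25, no covariate, and Rubin pooling with many imputations. Then T = W + B, where W is the usual variance of the mean in the completed data and B = (m/N)² × 625/m. For observed mean 8 and m = 9:

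- pooled mean = 360/54 = 6.667
- W = (27,500 + 5,625 + 2,880 − 2,400)/(53 × 54) = 11.742
- B = 9 × 625/54² = 1.929
- t = 6.667/√13.671 = 1.803, normal p = 0.036

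Allowing for uncertainty in the mean (adding (m/N)² × 625/45 to B) and using small-sample df raises p to 0.041. Over these variants, with 9 missing:

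| Observed mean | p, zero mean with spread | Mean change among the missing at which significance is lost |
|---|---|---|
| 8 | 0.036–0.041 | +3.3 to +5.1 mm |
| 10 | 0.012–0.016 | −4.1 to −5.8 mm |
| 13 | 0.002–0.003 | −16.4 to −18.0 mm |

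The largest observed mean overturned is 8.7 to 9.1 mm. The share of trials that are significant but overturned is 5.5–7.8% at a true mean of 13 and 11–15% at 10. A simulation with 50 imputations at a true mean of 13 gave 5.8–9.3%. As an upper bound, treating all 15 as ordinary missing values gives p of 0.049–0.059, 0.020–0.027 and 0.004–0.007 at means 8, 10 and 13.

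**The case against.** The strongest reply is about reach. The primary analysis uses no imputation, so the loop cannot alter it. At the planned 13 mm the result survives no-relief imputation with spread, and with 9 missing it is lost only if they worsen by 16 to 18 mm on average. The affected band, about 7.5 to 9 mm, arises in a small share of trials under the planning assumptions. This stands, and it limits the seriousness of the point, but it does not make the check informative.

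Second, zero is the null value and so a recognisable no-benefit assumption, and the falling mean would be visible if summaries were reported. That is true of the estimate. Section 11.8, however, judges the loop by significance and does not ask for those summaries.

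Third, random draws include some negative changes: about 30% at mean 13 and SD 25 if changes are normal. Their average is still the completers' benefit, so they do not test worsening.

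Fourth, the missing shares come from a recruitment allowance, and the visit procedures are redacted. For participants who do not reach the threshold, a post-application change may not exist, so the figures for all 15 are only an upper bound. Both caveats stand.

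**Conclusion.** The concern holds. With 45 observed changes, the zero loop cannot overturn a t-test result with one-sided p below 0.0244, and no planned analysis assumes that the missing worsened. The first statement is exact algebra and needs no distributional assumption; the second rests on section 11.8, which is readable on missing data.

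The practical cost falls on smaller observed effects, up to about 9 mm with 9 missing, where the loop reports an unchanged result that a no-relief assumption with realistic spread would overturn. That part assumes SD 25 among the missing and no help from Day 0 data, whose correlation with Day 45 the documents do not give. The planned 13 mm result is not shown to be fragile. This should be fixed, but it does not threaten the primary analysis.

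**What to change.** Replace the zero loop in section 11.8, or keep it as a descriptive summary that reports the attenuated mean, with the following beside it.

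- Multiply impute missing Day 45 changes with residual variance kept, using the Day 0 EDS change where available. Pool by Rubin's rules on the t-test scale, and state that this scale is used even if the signed-rank test is the primary test.
- Shift the imputed values in prespecified fixed steps, for example 5 mm, through zero mean change and on toward worsening. Report the shift at which one-sided p exceeds 0.025.
- Apply the shifts to participants who discontinued. Report those who did not reach the CAE application threshold separately; section 11.4 already counts the two reasons.

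The cost is SAP wording and a short program, with no new data, visits or participants. The downside is that a borderline result may be reported as less robust than under the current rule.

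### The random-donor sensitivity analysis in 11.8 has the observed-case mean as its expected result, so it repeats the primary analysis's missing-data assumption instead of testing it; drawing on each participant's Day 0 response would cost little

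*Combined protocol and SAP*

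**What the plan says.** The primary analysis (11.8) uses the FAS at Day 45 without imputation. Section 11.4 defines the FAS as "all participants who initiated at least one application of the TrueTear device at any point during the study", so it includes people with no Day 45 value.

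Section 11.6 sets the trigger for missing-data work: "A sensitivity analysis of the FAS population will only be conducted if" at least 5% of the primary results are missing. Section 11.8 then gives two imputation checks:

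- **Zero imputation.** The plan says "a sensitivity analysis of EDS difference at Day 45 will be performed by imputing the missing EDS difference as zero". This is done one participant at a time, stopping when significance is lost or everyone has been imputed.
- **Random donors.** The plan says "missing values will be imputed using a random selection process from the available Day 45 results and the analysis will be repeated". It continues: "This process will be performed 10 times and a single combined p-value for the 10 imputations will be obtained", using Rubin's rules and PROC MIANALYZE.

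No section makes the donor draw depend on Day 0 response, site, reason for missingness or anything else. Yet a Day 0 counterpart of the endpoint is collected: "The exploratory effectiveness variables will be the difference in EDS at Day 0". Section 8.2 places the first stimulation in the Day 0 CAE session, and Appendix 2 has EDS recorded on entry and every five minutes on both CAE days.

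Section 11.1 enrols 60 to obtain 45 Day 45 results: "In order to allow for participants that discontinue the study before Day 45 or do not reach the application threshold in the CAE".

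**The concern.** A missing-data sensitivity analysis should show what happens if the missing differ from the observed. An unconditional draw from the observed values assumes that they do not differ, and the observed-case primary analysis already assumes this. If people with little relief on Day 0 are more likely to be lost over 45 days of open-label home use, the observed mean is too favourable. The donor check would reproduce that mean and could be reported as confirming it. Having the right standard error would not help, because a fully proper version of the same unconditional draw has the same expected mean.

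What is at stake is the credibility of the robustness evidence and of the reported size of relief. The primary test itself is not affected.

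**Working it through.** **Inputs from 11.1:** reduction 13, SD 25, 45 analysed, 60 starting, one-sided α 0.025, about 10% missing the application threshold in an earlier study. **Assumed, because the documents are silent:** the Day 0/Day 45 correlation (0.3 to 0.7), dropout that depends on Day 0 relief, and a Day 0 gap between observed and missing participants of about 12 or 22 mm.

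**1. The plan's own figure.** The plan states: "Using an estimated standard deviation of 25, 45 participants will provide over 90% power to detect a EDS reduction of 13". The noncentrality is (13/25) × √45 = 3.49. The noncentral t gives 92.7% power, so the statement is reproduced.

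**2. Share missing.** The planned allowance is 15/60 = 25%. If about 10% of 60 (6 people) miss the threshold on Day 45, 15 − 6 = 9 are lost for other reasons, and 9/60 = 15%. This split is illustrative.

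**3. Expected result of the donor check.** With equal-probability draws, each imputed value has expectation m, the observed mean. The expected completed mean is (45m + 15m)/60 = m, whatever the missing participants' true responses. This needs no assumption about dropout. In simulation (45 observed, 15 missing, 10 imputations) the donor mean stayed within 0.02 mm of the observed mean. The pooled SE was about 3.60, against about 3.70 for the observed cases, so the check is not more cautious on precision either.

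**4. Size of the bias.** If loss depends on Day 0 relief, bias = missing share × correlation × Day 0 gap. In mm:

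| Missing | Gap | corr. 0.3 | corr. 0.5 | corr. 0.7 |
|---|---|---|---|---|
| 15% | 12 | 0.54 | 0.90 | 1.26 |
| 15% | 22 | 0.99 | 1.65 | 2.31 |
| 25% | 12 | 0.90 | 1.50 | 2.10 |
| 25% | 22 | 1.65 | 2.75 | 3.85 |

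Simulations with 60 participants, SD 25 and true mean 0 agree: about 0.5 to 2.4 mm at 15% and 0.9 to 3.9 mm at 25%. One-sided rejection by the donor check was about 4% to 11% and 5% to 21%, against 2.5% nominal. The unimputed primary test under the same assumptions rejected in about 3% to 11% and 4% to 17%. With zero correlation there is no bias.

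**5. The zero-imputation check.** Take 45 observed, mean 13, SD 25. The sum is 45 × 13 = 585 and the sum of squares is 44 × 625 + 45 × 169 = 35,105. Adding 15 zeros changes neither.

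- Mean: 585/60 = 9.75.
- SD: √[(35,105 − 585²/60)/59] = √(29,401/59) = 22.32.
- t: 9.75/(22.32/√60) = 3.38, against 3.49 before.
- One-sided p: 0.00064, against 0.00056 before.

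The estimate falls by a quarter while the p-value hardly moves. In simulation with a true mean of 0, this check rejected at essentially the observed-case rate.

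**6. Using Day 0.** With regression imputation on the Day 0 change, bias in the step 4 scenarios was about 0.1 mm and rejection about 2% to 4%. That simulation generated data from the same model it fitted, so it is a best case. A harder case has leavers truly getting 0 at both visits and the others 13, so the true FAS mean is (45 × 13 + 15 × 0)/60 = 9.75. Donors give 13.0 to 13.1. Day 0 regression gives 12.1, 11.5 and 10.7 at correlations 0.3, 0.5 and 0.7.

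**The case against.** The strongest reply is that the plan already has a pessimistic check. A reader might infer from the donor check's weakness that nothing in 11.8 responds to poor responders being lost. The documents do not support that: zero imputation gives every missing participant no relief. At a true mean of 13, in the step 4 scenarios, the fully imputed mean sits 0.5 to 2.6 mm below the truth with 25% missing. With 15% missing it lies between 1.5 mm below and about 0.05 mm above. This stands for the estimate. It does not stand for significance, which is how 11.8 decides when to stop imputing.

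Four further limits stand:

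- A reader might read the 4% to 17% rejection as a fault of this check. It belongs to the unimputed primary test, and changing a sensitivity analysis leaves it as it is.
- A reader might take 25% as the share lost through dropout. The allowance in 11.1 also covers people who attend but do not reach the threshold, and the redacted visit procedures do not show the split.
- That weak Day 0 responders leave more often is an assumption. The 22 mm gap exceeds the whole planned effect.
- At the planned effect the conclusion survives. Taking 3.9 mm off 13 leaves 9.1, so t = 9.1/(25/√45) = 2.44 and one-sided p is about 0.009.

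Day 0 conditioning is also only a partial remedy when loss depends on the unseen Day 45 response (step 6).

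**Conclusion.** The point holds as a minor one. That the donor check returns the observed-case mean in expectation is an identity and rests on no dropout assumption. The bias of about 0.5 to 2.4 mm (15% missing) or 0.9 to 3.9 mm (25%), and the donor check's rejection rates, rest on the assumed mechanism, gap and correlation, and vanish at zero correlation.

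The documents do not support the stronger conclusion that the trial's primary result is unsafe. No decision in the plan is tied to this check, and at 13 mm the bias would inflate the reported relief more than it would threaten significance. It could matter more if the Day 45 effect is small, and 11.1 says that effect is unknown. The case for change is that the planned check adds no information about selective loss, while data already collected would let it add some.

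**What to change.** In 11.8:

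- Replace the random draw with multiple imputation of the Day 45 EDS change, by regression or predictive mean matching on the Day 0 EDS change and the Day 0 pre-application EDS, combined with PROC MIANALYZE.
- Tabulate the Day 0 EDS change for participants with and without a Day 45 result. This shows directly whether loss was selective on Day 0 response.
- State whether participants who attend Day 45 but do not reach the application threshold are imputed or reported separately.
- Keep the zero-imputation check as the pessimistic companion, and report its estimate as well as its p-value.

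The cost is a paragraph of SAP text and a few lines of code, with no new data. The regression would rest on about 45 pairs, and a few missing Day 0 values may need imputing too. Nothing is gained if Day 0 and Day 45 responses are uncorrelated.
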